## Selection and Exclusion of Subjects

The participants are recruited through initial consultations at the university's neuropsychological outpatient clinic as well as through self-help groups and practitioners in the region involved in the aftercare of stroke survivors. For this purpose, information flyers are sent to neurological rehabilitation clinics as well as neurological, physiotherapy, occupational therapy, and speech therapy practices. Information and contact details for the study are also published on the homepage of the outpatient clinic and the research unit. Eligibility is evaluated by the principal investigator in an a-priori screening session using relative's information as additional source, if possible.

The study includes N = 12 adult individuals who:

1. have experienced a stroke (ischemic infarction or intracerebral hemorrhage);
2. report increased distress according to the DASS-21;
3. demonstrate sufficient cognitive and linguistic abilities; and
4. show sufficient motivation for therapy.

Increased distress according to the DASS-21 is defined as exceeding a cutoff on at least one of the three subscales of the questionnaire (Depression = D > 10, Anxiety = A > 6, and Stress = S > 10; Nilges & Essau, 2015). In the initial consultation, the cognitive and linguistic performance is assessed based on the participants' self-report and, if applicable, that of a family member, supplemented by the external judgment of the study leader, who has extensive experience in clinical work with individuals with brain damage. If the participant, possibly with input from a family member, and the study leader agree that the person can effectively participate in and benefit from 90-minute group therapy sessions on a weekly basis, the criterion is considered fulfilled. Finally, therapy motivation is assessed by participants assuring their willingness to change their approach to the illness, attend sessions regularly, and complete homework assignments within the therapy program as fully as possible.

Exclusion criteria are assessed based on self-report and external reports by the interested individual, the study leader, and possibly a family member, and include:

1. Interaction or behavioral disorders that significantly hinder group participation (e.g., significantly increased irritability or apathy);
2. Other severe psychiatric disorders (dementia, psychosis, personality disorder, intellectual disability); and
3. Simultaneous psychotherapeutic or neuropsychological treatment.

## Treatment of Subjects

Two study therapists lead a group, and the principal investigator serves as a therapist in both groups. The co-therapists are licensed psychotherapists. Table 1 provides an overview of the contents of the sessions and homework.

Table 1. Overview of Sessions and Homework

No.	Content	Homework
1	Introduction, Group Rules, Identification of Complaints, Formulation of Therapy Expectations, Exercise "What is in my Power?" (Derivation of ACT Therapy Rational)	Deepening Therapy Rational: Recognizing uncontrollable things in daily life, associated control strategies, and alternative coping methods
2	Introduction to Mindfulness, Connection with Therapy Rational, Body Scan Exercise with Reflection	Daily Body Scan Exercise, One-time "Mindful Meal" Exercise
3	Discussing the Function of Negative Emotions, Identifying Personal Negative Emotions and	Daily Body Scan Exercise, One-time "Mindful Daily Activity" Exercise

No. Content	Homework
Cognitions, Mindful Management of Unhelpful Experiences	
4 Identifying Individual Complaints and Control Strategies as a Review, Exercise "ACT-in-a-Nutshell"	Daily Body Scan Exercise, One-time "Mindful Daily Activity" Exercise, Recording Activities Possible After Stroke
5 Exercise "Mindfulness of Breath," Exercise "Passengers on the Bus" (Cognitive Defusion, Values Orientation), Introduction of Values and Identification of Personal Values with List, Formulation of Initial Approach Steps	Twice daily "Mindfulness of Breath" Exercise, One-time "Mindfulness for Sounds" Exercise, Naming Important Values and Initial Commitments
6 Development of Value-Concordant SMART Goals (Immediate, Short-term, Long-term)	Twice daily "Mindfulness of Breath" Exercise, Completing the Worksheet on Values and Goals
7 Reflection on Values and Goals, Identification of Cognitive Obstacles and Helpful Cognitions in Goal Achievement (Value-Based Life Planning)	Optionally daily Body Scan Exercise or twice daily "Mindfulness of Breath" Exercise
8 Reflection on Value-Based Life Planning and all Sessions, Exercise "Something Positive About..." Conclusion	Guidance on Implementing Value-Based Life Plan and Incorporating Mindfulness into Daily Life

## Assessment of Efficacy

Study design, sample size, and application of novel questionnaire versions do not allow to sufficiently prove efficacy of the treatment. However, first indicators of efficacy are investigated by pre-/post comparisons of psychological flexibility (AAQ-ABI) and psychological burden (DASS-21). As secondary outcomes, changes in valued living (VQ), self-as-context (SACS), depressive symptoms (PHQ-9), and anxiety symptoms (GAD-7) are examined. Statistically significant changes are considered indicators of efficacy. In addition, number of participants under the cut-offs on DASS-21 (D  $\leq$  10, A  $\leq$  6, S  $\leq$  10), PHQ-9 ( $\leq$  11), and GAD-7 ( $\leq$  11) before and after the therapy are assessed.

## Assessment of Safety and Adverse Events

In the screening session, presence of dysphagia is assessed via self-report to consider and adjust provision of drinks and/or snacks during the group therapy for individuals with impaired swallowing functions. Regarding all other physical health risks, legal and university internal protective measures are followed.

Severe adverse events (SAEs) are recorded after half of the sessions (end of session 4) and after the last session. SAEs include unplanned admissions to psychiatric ward, severe self-mutilating behavior with threat to life, suicide attempts, and death. There is also space on the questionnaire to report further burdensome events. If participants miss a session without giving notice, therapists contact them or relatives via telephone to exclude SAEs. After reporting a SAE, a study therapist immediately counsels the participant on treatment options. In case of death, relatives are offered counseling. Reporting of an SAE leads to immediate pausing of the study. Each SAE is then reported to two psychotherapists who do not participate in facilitating the study therapy. They assess whether a causal relationship between the SAE and the intervention is probable. If a probable relationship is determined, the study is immediately terminated.

Adverse events (AEs) are defined as an increase in documented symptoms of depression, anxiety, and stress, or the emergence of new symptoms by the end of therapy. Participants experiencing new symptoms are offered counseling on further treatment options. During the group therapy, participants may always approach therapists to report increased burden. Therapists may also decide to address suspected increase of burden in individual participants. In case of increased burden, participants are offered counselling on treatment options.

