## Study Design

The study employs a pre-post design without a control group. Consequently, there is no randomization or blinding to conditions. Group therapy is conducted with two groups, each consisting of six individuals. The therapy consists of 8 sessions, each lasting 90 minutes. A 30-minute diagnostic examination with questionnaires, including socio-demographic and health-related data, current psychopathology (depressive symptoms, PHQ-9; Kroenke et al., 2001; psychological burden, DASS-21; Lovibond & Lovibond, 1995; anxiety, GAD-7; Spitzer et al., 2006), and ACT-specific outcomes (valued living, VQ; Smout et al., 2014; psychological flexibility, AAQ-ABI; Sylvester, 2011; self-as-context, SACS; Zettle et al., 2018) takes place just before the first session. AAQ-ABI and SACS were translated into German for the first time according to recommendations using independent forward and backward translations (Wild et al., 2005). The questionnaires PHQ-9, DASS-21, GAD-7, AAQ-ABI, VQ, and SACS were also translated into plain language by a professional translation service ("Office for Easy Language Bethel", Bielefeld). After each session, participants and therapists rate the session using the GTS-P and the GTS-T, respectively. After the last session, all participants answer the same questionnaires as before the first session. They evaluate the entire therapy in the GTS-P and indicate if they would recommend the therapy to a friend with similar complaints (yes/no). The pre- and post-assessments are conducted by a trained assistant to exclude biases from the study therapists as facilitators. After the last session, therapists rate the entire therapy for each patient using the GTS-TP.

In a session form, therapists also record the participation of individual persons (Yes/No) and the completion of homework assignments (Yes/No/Incomplete) for each session. If not completed or incomplete, subjective obstacles are queried and documented. This serves to examine feasibility regarding session adherence and homework completion (objective 1).

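### SAE questions are scheduled only after sessions 4 and 8, so a serious event that no other route reveals can wait up to 4 weeks to be recorded

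*Combined protocol and SAP*

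**What the plan says.** Under Assessment of Safety and Adverse Events, the plan fixes two recording times: "Severe adverse events (SAEs) are recorded after half of the sessions (end of session 4) and after the last session". It defines the events of interest: "SAEs include unplanned admissions to psychiatric ward, severe self-mutilating behavior with threat to life, suicide attempts, and death".

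Three other routes are given in the same section:

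- A telephone check tied to unannounced absence: "If participants miss a session without giving notice, therapists contact them or relatives via telephone to exclude SAEs".
- Participant initiative: "During the group therapy, participants may always approach therapists to report increased burden".
- Therapist initiative: "Therapists may also decide to address suspected increase of burden in individual participants".

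The consequence of a report is strict: "Reporting of an SAE leads to immediate pausing of the study". Immediate counselling and an assessment of causality by two psychotherapists outside the study therapy also follow a report.

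Study Design describes what is collected every week. "After each session, participants and therapists rate the session using the GTS-P and the GTS-T, respectively". Also: "In a session form, therapists also record the participation of individual persons (Yes/No) and the completion of homework assignments (Yes/No/Incomplete) for each session". Where homework was not done or only partly done, the obstacles are asked about and written down. None of these instruments is described as asking about SAEs. Treatment of Subjects adds that two therapists lead each group and that the co-therapists are licensed psychotherapists.

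**The concern.** Counselling, the pause and the causality review all begin with a report. The plan schedules the SAE questions only twice in eight sessions. Someone who is absent without notice is telephoned specifically to rule out an SAE. Someone who attends, or who cancels with an uninformative reason, gets no equivalent check until the next scheduled form.

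The defined events include suicide attempts and life-threatening self-harm, in people selected for raised distress on the DASS-21. Concurrent psychotherapeutic or neuropsychological treatment is an exclusion criterion, so the trial cannot count on another current psychotherapist to notice. The symptom questionnaires are scheduled only before the first session and after the last, so they do not fill the interval either.

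What is at stake is mainly time. For an event that stays hidden, sessions continue while the safeguards wait. A secondary matter is the completeness of the SAE count.

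**Working it through.** **Inputs.** Eight sessions, in two groups of six (Study Design). Weekly spacing, which appears only in the eligibility text (Selection and Exclusion of Subjects). SAE recording at the end of session 4 and after the last session (Assessment of Safety and Adverse Events).

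**Plan's own figure.** Half of 8 sessions is 8/2 = 4, which agrees with the stated mid-point. The plan states no detection delay.

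**Calendar.** Put session s at week s − 1. Session 1 is at week 0, session 4 at week 3 and session 8 at week 7. The scheduled gaps are 3 − 0 = 3 weeks and 7 − 3 = 4 weeks.

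**Delay to scheduled recording**, for an event that no other route reveals and that is equally likely at any time over the 7 weeks:

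- Both forms completed: maximum 4 weeks; mean (3 × 1.5 + 4 × 2.0)/7 = 12.5/7 = 1.79 weeks.
- Session 4 form missed and not made up: maximum 7 weeks; mean 7/2 = 3.5 weeks.
- If 20% of participants lack the session 4 form (an illustration): 0.8 × 1.79 + 0.2 × 3.5 = 2.13 weeks.
- Asked at every session: maximum 1 week; mean 0.5 weeks.

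Each skipped week within a gap adds one week to its maximum. For someone who also never completes the final form, the plan states no limit.

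**Allowing for the informal routes.** Suppose a share q of SAEs comes to light by the next weekly session, with a mean delay of 0.5 weeks. The documents give no value for q, so a range is shown.

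| q | Both forms: 0.5q + 1.79(1 − q) | Session 4 form missed: 0.5q + 3.5(1 − q) |
|---|---|---|
| 25% | 1.46 | 2.75 |
| 50% | 1.14 | 2.00 |
| 75% | 0.82 | 1.25 |
| 90% | 0.63 | 0.80 |

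The comparison value is 0.5 weeks with questions at every session. With both forms completed, the mean saving is therefore about 1.0 week at q = 25% (1.46 − 0.5) and about 0.1 week at q = 90% (0.63 − 0.5).

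**Which events are left.** A death or psychiatric admission would usually show as an absence. Without notice, it triggers the call; with notice, the notice may explain it. What mainly remains is a suicide attempt or life-threatening self-harm without absence that the person does not volunteer, or an admission behind an uninformative cancellation.

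**The case against.** The strongest reply is that the long delays need several failures at once. The 4-week figure needs an event just after session 4 that the participant, two therapists, the absence call and weekly contact all fail to bring out. The 7-week figure also needs an event early in therapy, a session 4 absence with an uninformative notice, and no made-up form. The homework-obstacle query is a documented weekly enquiry, the therapists' discretion is clinical judgement, and severe psychiatric disorders such as psychosis and personality disorder are excluded. If most events surface within a week, the mean gain is a day or two. The remedy is also self-report: it helps only those who would answer a private form but would not speak up.

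Most of this stands, and it keeps the priority low. It does not close the gap. The homework query arises only when homework is incomplete and would reveal an SAE by chance. The exclusions lower the risk but leave people with raised distress in the study. The plan already accepts checking at session level for one kind of absence.

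A reader might go further than the documents allow in three ways:

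- That SAEs can be reported only twice, or that the schedule contradicts the immediate pause. Neither follows: participants may approach therapists at any time, and the pause runs from the report, whenever it comes.
- That the plan accepts a 7-week gap. The documents are silent on making up a missed form; they do not say it is skipped.
- That the SAE count will be incomplete. For a participant who completes the final form and discloses, an earlier event is still captured, only late. The count can fall short for people who do not complete that form and for completers who do not disclose. Whether people who withdraw are asked is not stated.

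**Conclusion.** The concern holds as a limited weakness in safety monitoring, of minor to moderate priority. An SAE hidden from every other route can wait up to 4 weeks for scheduled recording, with a mean of about 1.8. The maximum rises to 7 weeks (mean 3.5) only if session 4 is missed with notice and its form is not made up.

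These figures rest on strictly weekly sessions, a completed final form with disclosure, and, for the means, events spread evenly over therapy. All are conditional on an SAE occurring; the documents give no rate, so the expected number of affected participants among the 12 cannot be stated. The case for change is that the exposed events are grave and asking more often costs little, not that the present plan is unsafe or inconsistent.

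**What to change.** 1. After every session, put the existing SAE questions privately to each attending participant, on a sheet separate from the GTS-P so that safety answers are not mixed with acceptance ratings. A study therapist or the trained assistant reads it before the participant leaves; without prompt reading the 1-week maximum is not achieved.
2. Make up a missed session 4 or final SAE form by telephone.
3. Extend the existing telephone check to sessions missed with a notice that does not explain the absence.
4. Put the SAE questions to anyone who withdraws, at withdrawal and at the planned end of therapy.

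The SAE definition and the pause and termination rules stay as written. For participants who are reached and who disclose, the longest scheduled gap falls to about 1 week.

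**Cost.** Six sessions gain a form: 6 × 12 = 72 extra forms at full attendance, 72 × 0.8 ≈ 58 at 80%, and 72 × 0.6 ≈ 43 at 60%. At an assumed 1 to 2 minutes each, a full attender spends 6 to 12 more minutes over the therapy. Of 12 × 8 = 96 person-sessions, about 19 would be missed at 80% attendance and about 38 at 60%. Calls would be fewer where the notice explains the absence, and those after unannounced absence are already required. Leavers need two contacts each: 4 for two leavers, 8 for four. The 80% attendance figure is a feasibility target under test, so 60% is shown as well.

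**Downside.** Sensitive questions are repeated in a study that shortened its sessions partly to reduce cognitive load, and detection still depends on disclosure.

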## Statistical Analysis Plan

Missing values are replaced by multiple imputation including all assessed variables. Outliers are identified by visual inspection and inclusion/exclusion is decided on a case-by-case approach. Estimates are calculated based on 95% confidence intervals.

Feasibility (research question 1) is assessed by frequencies fulfilling the predefined cut-offs (see objectives).

The acceptance score of  $> 2$  is evaluated by Wilcoxon-tests for one sample (one-sided) for all versions of the GTS (-P mean of single sessions and entire therapy, -T, and -TP). Significant changes in primary outcomes psychological flexibility (AAQ-ABI) and psychological burden (DASS-21) are assessed with Wilcoxon-tests for paired samples (one-sided);  $p$ -value is Bonferroni-adjusted ( $p = .025$ ). Significant changes in secondary outcomes valued living (VQ), self-as-context (SACS), depressive symptoms (PHQ-9), and anxiety symptoms (GAD-7) are assessed with Wilcoxon-tests for paired samples (one-sided);  $p$ -value is Bonferroni-adjusted ( $p = .0125$ ). Individual changes in primary and secondary outcomes are also based on reliable change indices with a significance level of  $\alpha = .90$  (one-sided).

Sensitivity analyses examine the influence of the baseline variables age, gender, kind of stroke (ischemia vs. hemorrhage), current use of prescribed psychotropic drugs (yes/no), previous mental disorder (yes/no), and previous use of psychotherapy (yes/no) on changes in primary and secondary outcomes. These bivariate associations are investigated by Pearson correlations (for continuous covariates) and Chi tests (for categorical covariates;  $p = .05$ , two-sided) using the difference scores of the outcomes. Likewise, associations between therapy acceptance and the changes in efficacy outcomes (AAQ-ABI, DASS-21, VQ, SACS, PHQ-9 and GAD-7) are exploratively analyzed.

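### The adverse event definition has no instrument, minimum increase or combination rule; if a rise on any scale counts, noise alone would flag most participants

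*Combined protocol and SAP*

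**What the plan says.** The section Assessment of Safety and Adverse Events has two tiers. SAEs are a list of concrete events, and two psychotherapists who do not deliver the therapy judge causality. The second tier reads: "Adverse events (AEs) are defined as an increase in documented symptoms of depression, anxiety, and stress". Symptoms that first appear before therapy ends count as well. The section does not say which questionnaire documents the symptoms, how large an increase must be, or whether one symptom domain or all must rise.

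The only quantitative symptom records planned are the questionnaires given twice: "After the last session, all participants answer the same questionnaires as before the first session" (Study Design). They include the DASS-21 with its depression, anxiety and stress subscales. Among the secondary outcomes, "depressive symptoms (PHQ-9), and anxiety symptoms (GAD-7) are examined" (Assessment of Efficacy).

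The Statistical Analysis Plan does have a rule for individual change: "Individual changes in primary and secondary outcomes are also based on reliable change indices", at a level written as α = .90, one-sided. It does not link this rule to AEs, does not name the direction, and describes no AE analysis.

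On size and design: "The study includes N = 12 adult individuals who" meet the entry criteria, and "The study employs a pre-post design without a control group".

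**The concern.** Questionnaire scores move between two occasions even when the person has not changed. Without a minimum size, about half of such movements on any one scale are upward, and the chance that at least one of several scales goes up is higher still. With no control arm there is no background rate against which to judge the count.

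A harmless therapy could then be reported as having AEs in most participants, and one or two people who really deteriorated would be hidden among them. The plan has a tool for separating individual change from measurement error, but specifies it only for the outcomes. Placed beside one-sided tests for benefit, its most natural reading is improvement.

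**Working it through.** The documents state no AE rate, so there is no figure to reproduce.

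**Inputs from the documents.** N = 12; two assessments; three DASS-21 subscales, or five scores if PHQ-9 and GAD-7 count; no control arm; a one-sided reliable change level written as α = .90.

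**Assumptions, because the documents give none.** Change scores are normal with mean zero (no true change), equally correlated across scales with ρ from .3 to .7. Ties (no change) occur in a proportion t from 10 to 20% per scale.

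**Step 1: one scale.** P(rise) = (1 − t)/2, which is 45% at t = .10 and 40% at t = .20.

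**Step 2: at least one of k scales.** If the scales were independent, P = 1 − (1 − p)^k. For k = 3 and t = .10 this is 1 − .55³ = 83%. Correlation lowers it. Simulated values are:

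| ρ | ties | any of 3 | any of 5 | all 3 |
|---|---|---|---|---|
| .3 | 10% | 76% | 86% | 16% |
| .3 | 20% | 71% | 82% | 12% |
| .5 | 10% | 70% | 79% | 21% |
| .5 | 20% | 65% | 75% | 17% |
| .7 | 10% | 64% | 71% | 27% |
| .7 | 20% | 59% | 66% | 22% |

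Of 12 participants, the any-of-three reading flags 12 × .59 = 7.1 to 12 × .76 = 9.1. The any-of-five reading flags 12 × .66 = 7.9 to 12 × .86 = 10.3. Requiring all three flags 12 × .12 = 1.4 to 12 × .27 = 3.2.

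**Step 3: entry selection.** Participants enter by "exceeding a cutoff on at least one of the three subscales of the questionnaire", so regression to the mean should lower the rate of rises. A second simulation used integer subscales from 0 to 21 and the protocol's cutoffs, with assumed means, SDs, reliabilities and correlations. The any-of-three rate was 59-71% if the screening score is also the baseline, and 65-75% if baseline is measured separately.

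**Step 4: true change.** With a mean improvement of 0.5 SD of the change score, over the same ρ and tie ranges, the any-scale rate is 38-53% for three scores and 45-67% for five. With a mean worsening of 0.5 SD, at ρ = .5 and 10% ties, it is 87% for three scores, against 70% with no change. In 12 people that is 10.4 against 8.4. The binomial SD at 70% is √(12 × .70 × .30) = 1.6, so the difference of 2.0 is about 1.3 SD.

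**Step 5: a reliable-change limit.** A participant is flagged if any standardised change exceeds z in the direction of worsening. If α = .90 is read as a one-sided 90% limit, z = 1.28. Chance rates for ρ from .7 down to .3 are:

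| limit | any of 3 | of 12 | any of 5 | of 12 |
|---|---|---|---|---|
| z = 1.28 | 19-24% | 2.3-2.9 | 24-34% | 2.9-4.1 |
| z = 1.96 | 5-7% | 0.7-0.8 | 7-11% | 0.9-1.3 |

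These rates take measurement error as the only source of change. Real day-to-day fluctuation would raise them.

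**The case against.** The safety text does not say that a one-point rise on any of five scores is an AE. It names neither PHQ-9 nor GAD-7, and it joins the three symptom domains with an 'and'. Read as requiring all three to rise, chance flags about 12-27%; on a single scale, 40-45%. A reader might infer that most participants will be labelled with an AE whatever happens. The documents do not support that as a fact about the plan: it follows only on the any-scale reading and only without an average improvement. This objection stands. It also shows that the count has no fixed meaning until a reading is chosen.

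A reader might also infer that the study cannot show harm at all. That goes too far. SAEs are defined by events and reviewed independently, the SAE questionnaire has space for further burdensome events, and therapists may raise a suspected increase in burden. The weakness is confined to the AE count.

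The SAP sets out no AE analysis, and this is a small feasibility pilot. Both points limit the consequences. But the protocol defines AEs, so a count is likely to be reported and may inform a larger trial.

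Finally, reliable change is not a clean filter. At the plan's apparent 90% limit it still flags about two to four of 12 by chance. Subscale indices are not stated in the SAP, and an index needs a reliability estimate, which the documents do not give for the new plain-language versions. All of this stands and shapes the fix.

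**Conclusion.** The point holds in a limited form. The AE definition lacks an instrument, a minimum increase and a combination rule, and nothing in the SAP supplies them. Depending on the reading, the chance rate runs from about 12% (all three subscales must rise) to about 86% (any of five scores) under the assumed correlations and ties. On the any-scale reading, with 12 participants and no comparator, the AE count cannot separate deterioration from noise.

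The exact percentages rest on assumed correlations, ties and normality. Under no true change, the finding that an any-scale count flags more than half survives across the ranges tried, including entry selection. It need not survive a true improvement of 0.5 SD.

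**What to change.** Leave clinical management as it is and change only how the AE result is counted and reported.

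1. Name the scales that document depression, anxiety and stress, and state whether a rise on one scale is enough or all must rise.
2. Add to the safety results the number of participants with reliable worsening on DASS-21 depression, anxiety or stress, PHQ-9 or GAD-7, using the reliable change index in the direction of deterioration.
3. State the limit, clarifying what α = .90 means, and print the expected chance rate beside the count. A limit of 1.96 gives a much lower chance rate than 1.28 but misses more moderate deterioration.

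This needs no new participant data. It costs a second AE figure to explain, separate indices for the three DASS-21 subscales, and a sourced or assumed reliability for each scale. Where the reliability of a plain-language version is unknown, state the value used and show the count over a plausible range.
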